10.3 Treatment Procedure

Treatment procedure characteristics will be analyzed using the Safety analysis population.

Descriptive statistics or frequency distribution, as appropriate, by treatment group will be provided for the following:

- Pre-Treatment Characteristics (**Error! Reference source not found.**):
 - Head Condition
 - Scars or Lesions on Head
 - Was the subject "off" medication for at least 12 hours prior to the treatment?
- Vital Signs per Time Point (**Error! Reference source not found.**):
 - Systolic Blood Pressure
 - Diastolic Blood Pressure
 - Heart Rate
 - O₂ Saturation
- Treatment Characteristics (**Error! Reference source not found.**):
 - Time Inside Scanner
 - Sonication Treatment Time

- Target Size
- Minimal Energy
- Maximal Energy
- Number of Performed Sonifications
- Treated Side of the Body (Right / Left) (**Error! Reference source not found.**)
- Procedure Interruption / Early Termination:
 - Interruption:
 - Procedure interrupted for more than 30 minutes due to MR system problems (**Error! Reference source not found.**)
 - Procedure interrupted for more than 30 minutes due to ExAblate system problems (**Error! Reference source not found.**)
 - Listing of all device malfunctions (**Error! Reference source not found.**)
 - Early Termination:
 - Procedure terminated prior to completion (**Error! Reference source not found.**)
 - Listing of all termination reasons (**Error! Reference source not found.**)

10.4 Blinding Assessment

Blinding assessment will be analyzed using the Safety and Crossover analysis populations separately. Frequency distribution of subjective perception of treatment received by visit and treatment group will be provided (**Error! Reference source not found.**, **Error! Reference source not found.**, **Error! Reference source not found.**) for the following blinding assessments:

- Subject Perception
- Site Assessor Perception
- Core Lab Reviewer Perception

Where appropriate, Fisher's exact test will be conducted to compare subjective perception between treatment groups.

10.5 Safety

All safety analyses will be performed on the Safety and Crossover analysis populations – separately and combined, and will be descriptive and narrative in nature. Note that mock tables are presented for Safety population only. For Crossover and combined (Safety and Crossover) populations the tables will be prepared in the similar manner, presenting ExAblate group only. The following will be provided by treatment group:

- Adverse Events:
 - Descriptive statistics of Number of Adverse Events per Subject
(Error! Reference source not found.)
 - Frequency distribution of Experience of at Least One Adverse Event
(Error! Reference source not found.)
 - All Adverse Events (AEs) will be tabulated using Frequency tables with – Number of Incidents, Number of Subjects and Percentage of Subjects by:
 - Body System, Preferred Term and Resolution Time (within 30 days, within 31-90 days, more than 90 days), separately for Adverse Events started within 30 days post treatment, 31-90 days post treatment and more than 90 days post treatment
(Error! Reference source not found., Error! Reference source not found., Error! Reference source not found.).
Note that in case resolution date is missing, AE will be assigned to “Unresolved” category.
 - Body System, Preferred Term and Severity **(Error! Reference source not found.)**
 - Body System, Preferred Term and Relation to Treatment **(Error! Reference source not found.)**
 - Serious Adverse Events (SAEs):
 - Listing of all SAEs **(Error! Reference source not found.)**
 - In case the number of SAEs is greater than 12, all AE tables will be repeated, presenting SAEs only

- The Kaplan-Meier curve of AE's free percentage of subjects by time will be presented by treatment group. The groups will be compared using a Log-Rank test.

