2.1 Primary Endpoints

2.1.1 Safety

Safety of ExAblate will be determined by an evaluation of the incidence and severity of device / treatment related complications from the first treatment day visit through ALL study follow ups. Adverse events (type, frequency, severity) are expected to be similar to those of previous studies using ExAblate TcMRgFUS for Thalamotomy

All AEs will be reported and categorized by investigators as definitely, probably, possibly, or unrelated to the device or procedure and categorized by treatment group / treatment arm.

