4.1.2 ExAblate Test Arm Study Design

The randomized ExAblate Test Arm subjects will proceed to the ExAblate treatment. These ExAblate Test Arm subjects will then be followed up for 3-months post-ExAblate treatment to assess the study endpoints at study follow-up: 1day, 1week, 1 and 3 month visits. Subjects will be unblinded after the Month 3 assessments.

All subjects will be followed for 12-months post-treatment to assess the treatment long term safety and durability with study visits at 6 and 12 months.

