10.1 Subject Disposition

The following will be provided based on all recruited subjects:

- Subject disposition flow chart (Figure 1)
- Frequency distribution of answers (Yes / No) to inclusion / exclusion criteria
(Error! Reference source not found., Error! Reference source not found.)
- Frequency distribution of overall eligibility for the study (Yes / No) based on inclusion / exclusion answers **(Error! Reference source not found.)**
- Listing of screen failures along with the reason for not entering the study
(Error! Reference source not found.)
- Subject accountability by visit and treatment group **(Error! Reference source not found.)**
- By-subject listing of all protocol deviations **(Error! Reference source not found.)**

The following will be provided using Safety analysis population:

- Number and percentage of subjects in each of the analysis populations by treatment group (**Error! Reference source not found.**)
- Listing of subjects excluded from each of the analysis populations along with the reason for exclusion (**Error! Reference source not found.**)

The following will be provided using ITT analysis population:

- Number and percentage of subjects by center and treatment group (**Error! Reference source not found.**)
- Termination of the Study Main Stage:
 - Number and percentage of subjects who completed / prematurely discontinued the first 3 months FU of the study Main stage by treatment group (**Error! Reference source not found.**)
 - Number and percentage of subjects who completed / prematurely discontinued the follow up period (from 3 up to 12 months) of the study Main stage for ExAblate group only (**Error! Reference source not found.**)
 - Listing of all dropouts along with reason for termination, treatment group and last available visit (**Error! Reference source not found.**)

The following will be provided using Crossover analysis population:

- Number and percentage of subjects by center (**Error! Reference source not found.**)
- Termination of the Study Crossover Stage:
 - Number and percentage of subjects who completed / prematurely discontinued the study crossover stage (**Error! Reference source not found.**)
 - Listing of all dropouts along with reason for termination and last available visit (**Error! Reference source not found.**)
- Subject accountability by visit (**Error! Reference source not found.**)

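### The text of SAP 10.5 sets no onset window for four by-arm adverse-event displays, and for severity and relation no other planned table gives a like-for-like comparison

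*SAP*

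**What the plan says.** SAP 10.5 runs its safety analyses on the Safety population (and on the Crossover and combined populations, for ExAblate only) and calls them descriptive and narrative. By treatment group it lists:

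- "Descriptive statistics of Number of Adverse Events per Subject"
- "Frequency distribution of Experience of at Least One Adverse Event"
- AE frequency tables by "Body System, Preferred Term and Severity"
- AE frequency tables by "Body System, Preferred Term and Relation to Treatment"

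No onset window is stated for these four. A further set of tables, by body system, preferred term and resolution time, is split by onset at 0-30, 31-90 and more than 90 days. There is also a Kaplan-Meier display, in which the AE-"free percentage of subjects by time will be presented by treatment group", with a log-rank test but no stated censoring rule. If there are more than 12 serious AEs, all the AE tables are repeated for them. The Safety population in SAP 5.1 has no time limit.

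On follow-up, Protocol 4.1.2 says "All subjects will be followed for 12-months post-treatment to assess the treatment long term safety and durability". Under Protocol 4.1.3 Sham subjects are offered crossover at Month 3. SAP 10.7 has those who accept terminate the Main stage, and Protocol 4.2.2.3.1 puts their later data in a separate crossover database. SAP 10.1 reports completion of Months 3 to 12 of the Main stage for ExAblate only.

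Protocol 2.1.1 bases safety on the incidence and severity of "device / treatment related complications from the first treatment day visit through ALL study follow ups".

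**The concern.** An AE that starts in, say, Month 5 counts for an ExAblate subject in all four displays. A Sham subject who crossed over has left the Main stage by then and cannot contribute a matching event. Even with identical AE rates, the displays would tend to show more AEs on ExAblate.

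This matters because SAP Section 2 reserves the test of device safety for regulatory approval to the Main stage, and because the severity and relation tables correspond most closely to the protocol's safety measure. SAP 10.1 already separates the first three months, by arm, from Months 3 to 12, for ExAblate alone. SAP 10.5 does not carry that split into these displays. Nor does it say which period counts for Sham subjects who decline crossover or do not qualify, although Protocol Section 2 collects safety for one year after Sham or active treatment.

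**Working it through.** **The plan's own figures.** The plan states no AE rate by month and no expected by-arm difference. Its only safety probabilities (Protocol 5.4) are the chances of seeing at least one event. From 1-(1-rate)^n they come out at 0.954 (n=60), 0.901 (n=45) and 0.537 (n=15) for a 5% rate, and 0.453 (n=60) for a 1% rate. The stated values are 0.95, 0.90, 0.52 and 0.45. None bears on follow-up time.

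**What each output offers over a common window**

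| Display | Like-for-like view elsewhere in SAP 10.5? |
|---|---|
| At least one AE | Yes: one minus the Kaplan-Meier curve at day 90 |
| AEs per subject | Mean only: (incidents at 0-30 days + incidents at 31-90 days) / arm N |
| AEs by severity | No |
| AEs by relation | No |

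Incident counts add across onset windows. Subject counts do not, because one subject can appear in both.

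**Inputs for the size**
- From the documents: 12 months for ExAblate, about 3 months for crossed-over Sham, and 18 to 20 Sham subjects (one quarter of 72 to 80, Protocol 5.4).
- Assumed: p, the share of Sham crossing over; e0, early AEs per subject, the same in both arms; r, later AEs per subject-month, the same in both arms; Poisson counts; no device effect.

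**Formulas**
- Exposure ratio = 12/(12-9p)
- Ratio of AEs per subject = (e0+12r)/(e0+r(12-9p))
- Any-AE gap = p × exp(-e0) × [exp(-3r)-exp(-12r)]

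**Results** (ExAblate v Sham)

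| p | Exposure ratio | e0=2, r=0.10: AE ratio | Any-AE gap, points | e0=4, r=0.05: AE ratio | Any-AE gap, points |
|---|---|---|---|---|---|
| 1.00 | 4.0 | 3.20/2.30 = 1.39 | 5.9 | 4.60/4.15 = 1.11 | 0.6 |
| 0.75 | 2.3 | 3.20/2.525 = 1.27 | 4.5 | 4.60/4.2625 = 1.08 | 0.4 |
| 0.50 | 1.6 | 3.20/2.75 = 1.16 | 3.0 | 4.60/4.375 = 1.05 | 0.3 |

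The largest entry, at p=1, is exp(-2.3)-exp(-3.2) = 0.1003-0.0408 = 0.0595.

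**Upper limit on the any-AE gap.** exp(-3r)-exp(-12r) is largest at r = ln(4)/9 = 0.154, where it equals 0.4725. With p=1 the gap therefore cannot exceed 0.4725 × exp(-e0): 6.4 points at e0=2, 2.4 at e0=3 and 0.9 at e0=4.

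**Share of ExAblate AEs that start after Month 3** = 9r/(e0+12r): 0.90/3.20 = 28% at e0=2, r=0.10, and 0.45/4.60 = 10% at e0=4, r=0.05.

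**Bearing of the pilot.** In Protocol 1.4.2.1.2.4, 61 of 82 events in 15 subjects resolved within two weeks, or 61/15 = 4.1 per subject. That points to heavy early clustering, but the pilot had no sham arm, so it does not fix the early count shared by both arms.

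**The case against.** The case against has five parts, and most of it stands.

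- **Two of the four views are recoverable.** This is correct, as the working shows. A reader might infer that all four displays lack any common-window counterpart; only severity and relation do.
- **Background events should not reach the related rows.** Protocol 2.1.1 has investigators grade relation, so correctly attributed late background AEs fall in the unrelated rows. This weakens the point for the relation table. It does not help the severity table, because SAP 10.5 lists severity and relation as separate tables and does not cross them.
- **The protocol asks for full follow-up, and safety is descriptive.** Both are true. The full-follow-up tables are required and should stay. The gap is the lack of a comparable companion, and no success criterion depends on it.
- **The mock tables might carry a window.** They might, so the point is confined to the SAP text.
- **The size is small.** One Sham subject in 18 to 20 is 5.0 to 5.6 points, so the any-AE gap is about one Sham subject or less. "Subject accountability by visit and treatment group" in SAP 10.1 will also show how many Sham subjects remain after Month 3.

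A reader might also infer a fourfold excess of AEs on ExAblate from the 12 v 3 months. That needs every Sham subject to cross over and a constant AE rate from day 0. The documents do not give the crossover share, and the pilot's early clustering argues against a constant rate.

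**Conclusion.** The point holds in a limited form. Followed as written, SAP 10.5 would place up to 12 months of ExAblate AEs beside about 3 months for crossed-over Sham subjects in four displays, and for severity and relation nothing else in the section restores a fair comparison.

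With 50% to 100% crossover, 2 to 4 shared early AEs per subject and 0.05 to 0.10 later AEs per subject-month, the ratio of AEs per subject is 1.05 to 1.39 and the any-AE gap 0.3 to 5.9 points, with no device effect. All of these inputs are assumptions. The severity and relation tables would be distorted to a similar degree overall only if early and late events had a similar mix.

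The bias runs against the device. It would be a mistake to infer that the safety case is made to look falsely favourable, or that the safety data are lost or invalid: onset dates are recorded, and the gap is one of presentation. It is worth correcting because the correction is cheap.

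**What to change.** 1. For the between-arm comparison, add versions of the severity and relation tables limited in both arms to onset through day 90 after treatment, or up to crossover if earlier. For convenience, do the same for the any-AE and AEs-per-subject summaries and any serious-AE repeats. Day 90 matches the SAP's existing onset windows. A cut at the Month-3 visit, which may move by 14 days either way (Protocol 4.3), would not reconcile with them.
2. Keep the full-follow-up tables that Protocol 2.1.1 calls for, either labelled as unequal follow-up or shown for ExAblate alone after Month 3.
3. State that Sham subjects are censored at crossover in the Kaplan-Meier and log-rank analysis.
4. State which period counts for Sham subjects who do not cross over.
5. If the mock tables already carry a window, say so in the text of SAP 10.5.

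The cost is some SAP wording, one onset-date filter on existing programs and a few extra tables. No new data are needed.

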4.1.3 Sham Arm Study Design

The randomized, ExAblate Sham Arm subjects will proceed to the ExAblate sham treatment. This ExAblate sham treatment procedure will be identical to that of ExAblate Test Arm except the energy output will be disabled. These ExAblate Sham-treated subjects will then be followed up for 3-months post-ExAblate sham treatment to assess study endpoints; study follow-up: 1day, 1week, 1 and 3 month visits.

At the 3-Months time point after all visit evaluation have been performed, all ExAblate Sham-treated subjects will be unblinded and offered cross over to the actual ExAblate treatment as long as they still meet all inclusion/exclusion protocol criteria. They must exhibit a score of 2 or more on at least one of the Month 3 CRST questions 16-23 in order to continue to qualify. All these Crossover Arm ExAblate-treated subjects will be followed according to the same schedule as the ExAblate-treated Arm through the Month 12 post treatment study visit. Subjects may continue to be followed for an annual assessment through 5 years follow-up outside this protocol.

Note: at the time of the pre-Market submission, all available data of this cohort of crossed over subjects will be included in the submission.

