4.2.2.3.1 Sham Crossover

At Month 3, Sham subjects may be crossed over to ExAblate treatment as long as they continue to meet all the inclusion/exclusion criteria in the protocol. They must exhibit a score of 2 or more on at least one of the Month 3 CRST questions 16-23 and must score <20 on the PHQ-9 questionnaire in order to continue to qualify. All crossover data and follow-up will be captured in the Crossover Arm database for this study.

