4.3 Study Requirements and Visit Schedule

The table below summarizes the study visit schedule and procedures.

The study visits are as follows:

➤ Pre-treatment:

Baseline: 1 Month \pm 7 days post screening

➤ Post-treatment:

1 Week (i.e. 7 days) \pm 3 days, 1 Month \pm 7 days, 3 Month \pm 14 days (or 2 weeks), 6 Months \pm 21 days (or 3 weeks), 12 Months \pm 1 Month.

Table 4.2.2.3.2—1
Summary of Study Schedules and Measurements

| | Screening | Baseline | Treatment | 1 Day | 1 Week | 1 Month | 3 Month | 6 Month | 12 Month |
|---|-----------|----------|-----------|-------|--------|---------|---------|---------|----------|
| Consent | X | | | | | | | | |
| Eligibility Evaluation with labs | X | X | | | | | | | |
| Medications | X | X | X | X | X | X | X | X | X |
| 30 day meds stabilization | | X | | | | | | | |
| Medical History | X | | | | | | | | |
| Physical Exam | X | X | | X | X | X | X | X | X |
| Neurological status | X | | X | X | X | X | X | X | X |
| CRST (unblinded) | X | | | | | | X | X | |
| Site Blinded Assessor CRST | | X | | | | X | X | | |
| Blinded Tremor Core Lab CRST | | X | | | | X | X | X | X |
| QOL (QUEST) | X | X | | | | X | X | X | X |
| PHQ-9 | X | | | | | X | X | X | X |
| CT | X | | | | | | | | |
| MR | | X | X | | | | | | X |
| Treatment | | | X | | | | | | |
| Adverse Events | | | | X | X | X | X | X | X |
| Exit Form | | | | | | | | | X |

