10.7 Crossover Stage Analysis

The Crossover stage includes Sham subjects who terminated the Main stage of the study with the reason “Sham subject crossed over ExAblate Arm at Month 3”. According to the protocol, these subjects undergo Active ExAblate treatment and subsequent follow-up assessments, just as defined for the ExAblate group in the Main stage of the study.

All analyses in this section will be presented based on the Crossover analysis population. Results from the Main stage under Sham treatment will be presented in parallel with results under ExAblate treatment during Crossover stage, similarly to presentation of the Main stage results.

Descriptive statistics over time by treatment group will be provided for the following:

- Confirmatory primary and secondary efficacy endpoints
- Additional secondary endpoints

In addition, where appropriate, the following will be provided:

- Graphical presentation over time by treatment group
- Statistical testing to compare:
 - between treatment groups, by visit
 - within each treatment group, comparing Baseline to each follow-up visit
 - between treated and non-treated sides, within each treatment group, by visit

11 Data Listings

[figure not shown]
Data listings will be provided for all data available.

12 Appendix

The following section presents mock tables and figures for Section 10.

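### SAP 10.5 counts any adverse event without an end date as unresolved, with no cut-off common to the arms, so Sham events that outlast Month 3 may look more persistent than identical ExAblate events

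*SAP*

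**What the plan says.** SAP 10.5 tabulates AEs by treatment group using "Resolution Time (within 30 days, within 31-90 days, more than 90 days"), with separate tables for onset within 30 days, at 31-90 days and after 90 days. Each cell gives incidents, subjects and percentage of subjects. Events without an end date are handled by one rule: "Note that in case resolution date is missing, AE will be assigned to “Unresolved” category". The section has no common cut-off, no censoring at last contact and no category for events still open when follow-up stops. SAP section 7 leaves missing data in the Safety population unimputed.

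Planned follow-up differs by arm:

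- **Sham.** Protocol 4.1.3: "These ExAblate Sham-treated subjects will then be followed up for 3-months post-ExAblate sham treatment to assess study endpoints". Crossover is then offered. SAP 10.7 treats those who accept as having left the Main stage: "The Crossover stage includes Sham subjects who terminated the Main stage of the study with the reason", the reason being crossover at Month 3.
- **ExAblate.** Protocol 4.1.2: "All subjects will be followed for 12-months post-treatment to assess the treatment long term safety and durability". SAP 10.1 describes "the follow up period (from 3 up to 12 months) of the study Main stage for ExAblate group only".
- **After crossover.** Protocol 4.2.2.3.1: "All crossover data and follow-up will be captured in the Crossover Arm database for this study".

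Protocol 4.3 allows the Month 3 visit 14 days either way.

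**The concern.** Whether an AE has an end date depends partly on how long the subject is observed after onset. The rule makes no allowance for that, so a difference in follow-up can be reported as a difference in clinical outcome. Splitting the tables by onset period does not help, because the imbalance lies in the time after onset.

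How long events persist is a central safety question for a permanent lesion, and protocol 6.2 itself uses time to resolution to separate non-significant from significant side effects. SAP section 2 reserves the Main stage for testing device safety for approval, so the Main-stage tables by arm are the ones that will be read. If Sham events are over-counted as unresolved, ExAblate events look shorter-lived by comparison.

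**Working it through.** The documents give no expected share of unresolved AEs, so there is no planned figure to reproduce.

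**1. Observable duration.** Taking 3 months as day 90, the Sham exit falls between 90 − 14 = day 76 and 90 + 14 = day 104. ExAblate runs to about day 365. Observable duration is exit day minus onset day.

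| Onset day | Sham, exit day 90 | Sham, exit day 104 | ExAblate, day 365 |
|---|---|---|---|
| 0 | 90 | 104 | 365 |
| 30 | 60 | 74 | 335 |
| 60 | 30 | 44 | 305 |

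For onset on day 31 or later, a crossed-over Sham subject has at most 104 − 31 = 73 days in the Main stage. The cell for more than 90 days cannot be reached there. For onset on day 0 to 13 it can be reached only if the Month 3 visit is late.

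**2. One event, two labels.** Take onset on day 30 and duration 100 days, so resolution on day 130. In ExAblate it is resolved, in more than 90 days (whether counted from onset or from treatment). In a crossed-over Sham subject whose record stops by day 104, it is unresolved.

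**3. Illustration with the pilot pattern.** Protocol 1.4.2.1.2.4 reports, for 82 pilot events, 49% resolved the same day, 61/82 = 74% by two weeks, 14/82 = 17% later and 7/82 = 9% ongoing. Assumptions: the same pattern in both arms, counted from onset; late resolvers spread evenly from day 14 to day L; no write-back of end dates.

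For 14 ≤ t < L, the share unresolved t days after onset is U(t) = 1 − [61/82 + (14/82) × (t − 14)/(L − 14)]. For t ≥ L it is 7/82 = 8.5%. From day 1 to day 14 the resolved share rises evenly from 49% to 61/82.

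Onset day 0, Sham exit day 90:
- L = 60 or 90: U = 8.5%, excess 0.
- L = 180: 1 − [0.744 + 0.171 × 76/166] = 17.8%, excess 9.3 points.
- L = 300: 1 − [0.744 + 0.171 × 76/286] = 21.1%, excess 12.6 points.

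Onset spread evenly over days 31-90, averaging U(exit − onset):

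| L (days) | Sham, exit day 90 | Sham, exit day 104 | ExAblate, day 365 |
|---|---|---|---|
| 60 | 22.5% | 15.2% | 8.5% |
| 90 | 25.0% | 19.0% | 8.5% |
| 180 | 27.1% | 22.6% | 8.5% |
| 300 | 27.8% | 23.8% | 8.9% |

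The excess is 14 to 19 points at a day 90 exit and 7 to 15 at day 104. An exit at day 76 raises the Sham share to 26% to 29% of events that start by then.

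**4. A different duration model.** With exponential durations of median m (assumed), the share unresolved is 0.5^((exit − onset)/m). For onset on day 30, Sham at day 90 against ExAblate at day 365 gives 25% against 0% (m = 30), 50% against 2% (m = 60) and 63% against 8% (m = 90). The direction is the same; the size depends on the assumed durations.

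**5. The planned metric.** Steps 3 and 4 give shares of events, whereas the SAP reports percentages of subjects. At 3:1, 72 to 80 randomised subjects give 18 to 20 Sham subjects, so one subject with a relabelled event moves the Sham percentage by 100/20 = 5.0 to 100/18 = 5.6 points.

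**The case against.** The strongest reply is that the artefact arises only if end dates found after crossover are lost, and the protocol points the other way. Section 2 plans safety collection for one year after sham or active treatment. Section 6.6 has ongoing AEs reviewed at later visits and given an end date. Crossed-over subjects remain in scheduled follow-up under section 4.1.3, and section 4.2.2.3.1 does not say that open Sham-period records are closed. This stands as a limit on the claim: a reader might infer that the plan discards these dates, and it does not say that. But neither does the SAP say that a date recorded in the Crossover database updates the Main-stage record, and its wording treats the Main stage as finished for these subjects.

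The percentages are also borrowed. The pilot subjects had lesions, whereas sham subjects receive no energy, and the pilot times run from the procedure rather than from a late onset. No document gives the number of late-onset Sham events. The 14 to 19 points cannot be read as an expected bias in the SAP's tables.

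Finally, SAP 10.5 is descriptive. No test is applied to resolution, the log-rank test concerns AE-free time, and the listings and accountability tables would reveal the Sham exit. All of this stands and limits the consequence.

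**Conclusion.** The point holds in a conditional form. As written, SAP 10.5 allows identical AEs to be classed differently by arm when a Sham-period event outlasts the subject's Main-stage exit and its end date is not carried back. Events that resolve before the Sham exit are unaffected. The exit at Month 3 is explicit for subjects who cross over. For Sham subjects who do not, it rests on protocol 4.1.3 and SAP 10.1, and protocol section 2 reads differently.

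The direction is known: any artefact adds unresolved events to Sham and favours the device in the by-arm comparison. The size is not known; the figures above are hypothetical and fall to zero for day 0 onsets under two of the four spreads tried.

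A reader might go further and infer that the persistence of ExAblate's own events is understated, or that a confirmatory result is at risk. The documents support neither: ExAblate counts through Month 12 do not depend on Sham follow-up, and no confirmatory test uses resolution. This is an inexpensive improvement to a descriptive table.

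**What to change.** In SAP 10.5:

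1. For the by-arm table, classify Main-stage AEs in both arms by status at the Month 3 visit: resolved within 30 days, resolved later but by Month 3, or ongoing at Month 3. With a common cut, identical events get the same label in both arms.
2. Keep the existing resolution categories through Month 12 in a separate ExAblate-only table.
3. State that end dates of Sham-period AEs found after crossover update the Main-stage AE record.
4. Label events that remain open as ongoing at last contact, and show the days observed since onset.

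The cost is SAP wording, some table programming and linking AE records across the two databases. No new data are needed. The by-arm view of resolution beyond Month 3 is given up; it stays available for ExAblate alone.
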